5.4 Participant Withdrawal or termination

5.4.1 Reasons for Withdrawal or Termination

If a subject is discontinued at any time after Baseline (V2), the investigator will make every effort to see the subject and complete the final in-clinic study visit (V6) as soon as possible, ideally within one week of discontinuation of the other scheduled study procedures. A follow-up telephone call will still be attempted 4 weeks later.

Subjects may withdraw from the study at any time without stating a reason and without prejudice to further treatment. The Investigator may withdraw a subject from the study and discontinue study treatment and assessments at any time.

Early discontinuation of any subject who has given informed consent to participate will be recorded including the reason for discontinuation. The primary reason for a subject withdrawing prematurely will be selected from the following standard categories of early discontinuations:

- Failed to meet enrollment criteria.
- Adverse Event: Clinical events occurred or laboratory results are reported that in the medical judgment of the investigator are grounds for discontinuation in the best interests of the subject.
- Withdrawal of Consent: The subject desired to withdraw from further participation in the study. The subject is not obliged to provide any reason for withdrawal of consent, but where a reason is given this will be recorded on the CRF.
- Protocol Violation: The subject failed to adhere to the protocol requirements, at the investigator's discretion
- Lost to Follow-Up: The subject stopped coming for visits and study personnel were unable to contact the subject or caregiver. Every effort should be made to re-contact the subject prior to declaring a subject as lost to follow-up, which must be at least 3 documented attempts. The 3rd must be in writing and confirmed to have been received (e.g. registered post).
- Other: The subject was terminated for a reason other than those listed above, such as termination of study.

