4.2 Study Endpoints

4.2.1 Primary Endpoint:

- The incidence of Adverse Events (AEs) including Serious Adverse Events (SAEs) between Baseline and Week 8.
- The incidence of abnormal findings in objective assessments (e.g. laboratory values, ECGs, vital signs)

4.2.2 Secondary Endpoints:

- Seizure frequency as measured by a caregiver-completed seizure diary
- Syndrome-specific Clinical Global Impressions Improvement Scale (CGI-I)
- Clinician-completed PMS domain specific causes for concerns visual analogue scale (VAS)
- Top 3 caregiver Concerns VAS
- Aberrant Behavior Checklist (ABC) score
- Repetitive Behavior Scale- Revised (RBS-R) score
- Eye-tracking time on relevant target
- Change in phosphorylated ERK levels
- Telephone follow-up questionnaire

4.2.3 Exploratory Endpoints:

- Sensory Assessment for Neurodevelopmental Disorders (SAND)
- Electroencephalography (EEG)
- Auditory Evoked Potential (AEP)
- Visual Evoked Potential (VEP)

5. Study Enrollment and Withdrawal

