6.1.9 Duration of Therapy

The expected duration of participation is 12 weeks. Participation for individual subjects will consist of up to 4 weeks of an initial Screening period followed by a Baseline Day 0 visit. At this visit, if the subject is eligible they will receive a single 6-hour intravenous infusion for a total dose administered of 120 mg/m² of AMO-01. Subjects will return for follow-up visits at 1 day and 1, 2 and 4 weeks post-dose. A follow-up phone call will be conducted 8 weeks post-dose.

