7.1.15 Follow-up Telephone Call

The follow-up telephone call will be conducted by the study clinician and will address the following questions:

- 1. If applicable, is the participant's seizure activity the same, worse, or better than recorded at Week 4?
- 2. Are there any other clinical changes since Week 4?

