7.3.4 Final In-Clinic Study Visit

A final in-clinic study visit (V6) will be conducted 4 weeks post-dose. Refer to the schedule of events (Table 1) for a list of assessments to be completed at this visit.

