7.3.5 Early Termination Visit

In the event of early termination or withdrawal, the subject will complete the assessments scheduled for the final in-clinic study visit (V6). The follow-up phone call will also be attempted. Refer to the schedule of events (Table 1) for a list of assessments to be completed at this visit.

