8.3 Time Period and Frequency for Event Assessment and Follow-Up

All AEs occurring from screening (V1) until the time of the follow-up phone call 8 weeks after study drug administration will be recorded on the Adverse Event form in the subject's CRF, irrespective of severity or whether or not they are considered medication-related. Onset of chronic illness (e.g. autoimmune disorders, asthma, type 1 diabetes and allergies) and conditions prompting emergency room (ER) visits or physician office visits that are not related to well-child care, injury, or common acute illnesses (e.g., upper respiratory tract infection, otitis media, pharyngitis, and gastroenteritis) will be reported during the entire study period. The investigator will inquire about the occurrence of AEs at every visit/contact during the study and throughout the follow-up phase as appropriate. All AEs either observed by the investigator or a clinical collaborator or reported by the subject's parent/guardian spontaneously or in response to a direct question will be evaluated by the investigator. AEs not previously documented in the study will be recorded in the Adverse Event form within the subject's CRF. The nature of each event, date and time (where appropriate) of onset, outcome, intensity and relationship to drug administration should be established. Details of any corrective treatment should be recorded on the appropriate page of the CRF.

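### For subjects withdrawn during follow-up before about Week 4, Section 5.4.1 read naturally puts the last adverse-event call before Week 8, in conflict with the Baseline-to-Week-8 primary safety window

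*Combined protocol and SAP*

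**What the plan says.** Several sections set the end of AE observation at Week 8 after dosing:

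- Section 4.2.1 (primary endpoint): "The incidence of Adverse Events (AEs) including Serious Adverse Events (SAEs) between Baseline and Week 8".
- Section 8.3: "All AEs occurring from screening (V1) until the time of the follow-up phone call 8 weeks after study drug administration will be recorded".
- Section 6.1.9: "A follow-up phone call will be conducted 8 weeks post-dose". Table 1 lists AE collection at that contact (V7).
- Section 7.3.4 fixes the preceding visit: "A final in-clinic study visit (V6) will be conducted 4 weeks post-dose".

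For subjects who leave after Baseline, the text differs:

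- Section 5.4.1 asks the site to "complete the final in-clinic study visit (V6) as soon as possible, ideally within one week of discontinuation of the other scheduled study procedures", and continues: "A follow-up telephone call will still be attempted 4 weeks later".
- Section 7.3.5 (Early Termination Visit) says only "The follow-up phone call will also be attempted", without a time.
- Sections 5.4.2, 5.5 and 8.5 separate two groups. Subjects withdrawn during treatment are asked to continue safety assessments and follow-up on the protocol schedule, which includes Week 8. Subjects withdrawn in the screening or observation phases are asked only for an end-of-study visit.

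**The concern.** A 4-week interval after V6 matches Week 8 only when V6 is at its scheduled Week 4. Section 5.4.1 keeps the interval but moves the visit, so the call moves with it.

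Treatment is one 6-hour infusion, so nearly all withdrawals after dosing will fall in the observation phase. For that group Section 5.4.1 is the only text that times the last contact after withdrawal.

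The primary endpoint is at stake. Section 10.4.2 tabulates AEs and describes no adjustment for observation time. Section 8.5 keeps withdrawn subjects in all analyses. A subject last contacted around Day 30 would therefore count in the denominator in the same way as one followed to Day 56. A new event starting after the early call would have no scheduled occasion on which to be reported. With at most 10 subjects dosed, a single missed event matters to the reported incidence.

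**Working it through.** This is calendar arithmetic; no sampling formula is involved.

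**Inputs**

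- Primary window: Baseline to Week 8, that is 8 × 7 = 56 days (4.2.1, 8.3).
- Scheduled V6: Week 4, Day 28 (7.3.4).
- Interval from V6 to the call: 4 weeks, 28 days (5.4.1).
- *d*: day of discontinuation, with the infusion on Day 0.
- *L*: days from discontinuation to the early V6. Section 5.4.1 gives 0–7 as the ideal, not as a cap.
- Number dosed: up to 10 (4.1).

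**Reproducing the plan's own figure.** For a completer, Day 28 + 28 = Day 56, which is the stated Week 8.

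**Early leaver under 5.4.1**

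- Call day = *d* + *L* + 28.
- Days without a scheduled contact = max(0, 56 − call day) = max(0, 28 − *d* − *L*).
- Share of the window = those days / 56.

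| Discontinued | *L* = 0: call day; days uncovered | *L* = 7: call day; days uncovered |
|---|---|---|
| Day 1 | Day 29; 27 (48.2%) | Day 36; 20 (35.7%) |
| Day 7 | Day 35; 21 (37.5%) | Day 42; 14 (25.0%) |
| Day 14 | Day 42; 14 (25.0%) | Day 49; 7 (12.5%) |
| Day 21 | Day 49; 7 (12.5%) | Day 56; 0 |
| Day 28 | Day 56; 0 | Day 63; 0 |

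Nothing is uncovered once *d* + *L* is 28 or more, whatever the combination. Day 24 with a 4-day lag, for example, gives a call on Day 56.

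**Typical size.** The plan gives no dropout pattern. If discontinuations were spread evenly over Days 1–27 (an assumption), the mean uncovered time is 14.0 days (25%) with *L* = 0 and 7.8 days (13.9%) with *L* = 7.

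**Share of the whole study.** Ten subjects followed for 56 days give 560 person-days. One Day 1 leaver with no lag removes 27/560 = 4.8%.

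**Sensitivity to the unnamed starting point.** If the 4 weeks run from discontinuation, the *L* = 0 column applies. If they were meant to run from the scheduled Week 4, the call is on Day 56 and nothing is lost, but the text does not say so.

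**The case against.** The strongest reply is that other text already protects the window. Section 8.3 requires all AEs to be recorded to 8 weeks after dosing, with no exception for early leavers. Section 7.3.5 can be read as meaning the ordinary Week 8 call, since that is the only call defined elsewhere. Section 7.3.6 allows unscheduled visits for safety. Sections 5.4.2, 5.5 and 8.5 ask subjects withdrawn during treatment to follow the full schedule.

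Much of this stands, and it rules out three stronger readings that a reader might infer.

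- *Up to half of the window is never collected.* Exactly 28 of 56 days needs both discontinuation and the V6 assessments on Day 0. Subjects withdrawn during the infusion that day are asked to follow the protocol schedule. For observation-phase leavers from Day 1 onward, the maximum is about 48%. Because Section 8.3 still requires recording to Week 8, the documents show a conflict about the last contact, not a settled loss of data.
- *Incidence is biased downward for those who leave because of an AE.* Such a subject already has a recorded event, and Section 10.4.5 brings tolerability dropouts into the safety analysis. What could be missed is a further, new event that starts after the early call.
- *Early leavers have nothing to compare with at the call.* Section 7.1.15 asks "is the participant's seizure activity the same, worse, or better than recorded at Week 4". Section 7.3.5 has early leavers complete the V6 assessments, and Table 1 includes diary review there, so a record exists and only the label is inexact. The question concerns seizures, not the AE window.

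The reply does not remove the conflict. Recording to Week 8 needs a contact at Week 8. For observation-phase leavers the only sentence that times a call after withdrawal is the one in 5.4.1, and 5.4.2 asks them for nothing beyond an end-of-study visit.

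**Conclusion.** The point holds as an internal conflict with a bounded effect on the primary endpoint. For subjects withdrawn in the observation phase before about Week 4, the natural reading of Section 5.4.1 ends scheduled AE contact before Week 8, contrary to 4.2.1, 6.1.9 and 8.3.

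The gap is at most about 48% of the window for a Day 1 leaver and falls to zero by Week 4. This rests on three assumptions: the 4 weeks run from the early V6 or from discontinuation; sites follow 5.4.1 literally; and the early visit takes place within a week. A longer lag shortens the gap.

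The number of subjects affected is unknown because no dropout rate is given. If nobody leaves before Week 4, there is no effect. It should be corrected: a stated rule shortens the primary safety window for some dosed subjects, and the correction costs very little.

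**What to change.** Reconcile 5.4.1, 5.4.2 and 7.3.5 with 4.2.1 and 8.3. State that the final AE telephone contact for every dosed subject who consents and can be reached is at Week 8 after the infusion, whatever the date of the early V6. Make the matching passages in 5.5 and 8.5 consistent with this for observation-phase withdrawals. As an optional tidy-up, let question 1 of the call refer, for early leavers, to the last recorded diary period.

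With this change the call falls on Day 56 for any *d* and *L*, so the uncovered time is 0 of 56 days for those reached.

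The cost is a few sentences and no extra contact. The downside is a slightly higher chance of not reaching the subject, because the same single call comes later after withdrawal. No wording can secure data from a subject who has withdrawn consent to further contact.

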5.4.2 Handling of Participant Withdrawals or termination

If a subject is withdrawn from active study during screening or observation phases of the study, they will be returned to the referring physician and standard care will be recommended; in addition we will request the subject's participation in an end-of-study visit.

If a subject is withdrawn from active study during active treatment, they will also be returned to the referring physician and standard care will be recommended; however, in this case, we will in addition

request the subject's participation in clinical and laboratory safety assessments and follow up per protocol schedule.

5.5 Premature Termination or Suspension of Study

The following criteria will be used to identify possible adverse treatment events, which will indicate the need to halt active participation of the subject:

- Withdrawal of Consent
- PI or any regulatory authority (Safety Monitoring Board, IRB) believe withdrawal is necessary for the subject's health, well-being, or best interests.
- Any serious related AE of any sort (clinical, laboratory) \geq 4 will result in halting for the individual and also for the study as a whole.

Return of a subject to active study participation will not be permitted, except if a transient clinical or laboratory abnormality unrelated to study treatment has occurred and subsequent permission of the Safety Monitoring Board to return the patient to active study has been provided.

If a subject is withdrawn from active study during screening or observation phases of the study, they will be returned to the referring physician and standard care will be recommended; in addition we will request the subject's participation in an end-of-study visit

If a subject is withdrawn from active study during treatment, they will also be returned to the referring physician and standard care will be recommended; however, in this case, we will request the subject's participation in clinical and laboratory safety assessments and follow up per protocol schedule.

The study will be halted* if two patients experience stopping conditions across sites. (Exceptions for this criterion: Patients who withdraw voluntarily for reasons not directly related to or intrinsic to the study, e.g. incidental considerations such as concerns about travel time to study visits, unexpected pregnancy in the family, etc. In addition, the study will be halted if one patient experiences a serious related adverse effect (grade \geq 4 AE).

All safety data will be reported to the Safety Monitoring Board and IRB every six months, or, in the case of any major safety concern or question, immediately. If any study stopping condition occurs, this will be reported immediately and the study halted, pending review by the Safety Monitoring Board and IRB, and until the decision by regulatory authorities to resume, suspend or close the study has been made.

*Operationally, "halting" will ordinarily mean that no further screening of new subjects and no treatment initiation will occur until the safety issue has been investigated and resolved (i.e., a final decision has been made to resume, suspend or close the study has been made). Enrolled study participants who have no new symptoms or adverse effects will ordinarily be allowed to continue study observation or treatment without interruption while the safety issue is being investigated, unless it is the contemporaneous judgment of the PI or subsequent judgment of the Safety Monitoring Board or IRB that it is unsafe to do so, in which case all observation or treatment interventions will be suspended forthwith.

6 Study Agent and Administration

6.1 Study Agent

AMO-01 Chemical Name: 4,6,8-trihydroxy-10-(3,7,11-trimethyldodeca -2,6,10-trienyl)-5,10 dihydrodibenzo[b,e][1,4]diazepin-11-one

The Investigational Medicinal Product (IMP) is AMO-01 70mg sterile bulk drug product vials. Each vial contains 70 mg of AMO-01 drug substance in 2.134 mL of formulation (plus 2% overage). This corresponds to a total drug content of 71.4 mg of active drug substance per 2.176mL of formulation.

6.1.1 Acquisition

IMP will be provided by AMO Pharma directly to the Investigational Research Pharmacy for storage, preparation, and eventually dispensation.

6.1.2 Formulation, Appearance, Packaging, and Labeling

Formulation

The bulk IMP is a homogeneous liquid in which AMO-01 is dissolved. The appearance is a yellow to brownish yellow viscous liquid. The bulk IMP must be diluted in sterile 0.9% saline solution to produce an isotonic final dosing formulation prior to administration to study subjects.

The AMO-01 bulk vial formulation components are listed in Table 4.

Ingredient	Grade	Function	Fill Content ¹ (mg/vial)	Concentration (% w/w)	Reference Standard
AMO-01	cGMP	Active Ingredient	71.4	3.15	Manufacturer's Standard
Polysorbate 80	NF	Excipient	1249.5	55.15	NF
Polyethylene glycol 400	USP/NF	Excipient	357.0	15.76	USP/NF
Absolute Ethanol	USP	Excipient	282.0	12.45	USP
Water for Injection	USP	Excipient	282.0	12.45	USP
(+)-Sodium L- Ascorbate	USP	Antioxidant	23.6 ²	1.04	USP
TOTAL			2265.5	100.00	

Table 4: Bulk Formulation Components

¹Fill content corresponds to the true content in the vial, taking into account the overage. $^{2}(+)$ -Sodium L-ascorbate label claim and fill content correspond to amount initially present in bulk formulation (i.e. preservative).

The bulk IMP is provided by AMO Pharma in 30-mL sterile, pyrogen-free borosilicate clear glass vials (USP Type I vial), closed with a sterile teflon-coated butyl stopper, and crimp sealed with an aluminum seal.

Each bulk vial is individually labeled. At minimum, the label shall provide the following information: drug product name, label claim for strength per vial (including dose, concentration, volume and overage), professed sterility, manufacturing lot number, storage conditions and retest/expiry date.

6.1.3 Product Storage and Stability

Bulk Product Stability

Formal stability studies indicate that the bulk drug product is chemically stable over at least 12 months when stored at $5 \pm 3^{\circ}$ C. Therefore the recommended long term storage conditions for the DP is USP refrigeration, 2-8°C.

In-Use Stability

Stability of the final dosing formulation was evaluated in both ethylene-vinyl acetate (EVA) and polypropylene (PP) infusion bags and in the final diluted drug product vial. The results obtained with the EVA or PP infusion

bags at drug concentrations of 4.49 mg/mL demonstrated stability of the final dosing formulation for 7 days when refrigerated or stored at ambient temperature (15-30°C). The final dosing formulation (4.49 mg/mL), when placed in 100mL borosilicate vials, was also stable for 7 days when refrigerated or stored at ambient temperature.

Storage and Transport

Bulk formulation vials are to be stored at 5 ± 3 °C, and protected from light. Although in-use stability confirms acceptable stability of the final formulation for up to 7 days, it is preferable that the final AMO-01 formulation be prepared as close to the planned dosing time as possible in order to minimize the time that the drug is in the prepared final formulation state (ideally not more than 48 hours before dosing). Any prepared final formulation should be stored at 5 ± 3 °C, and protected from light until ready to dose within 48 hours of dilution.

Special Precautions

Since AMO-01 is a cytotoxic agent, procedures for proper handling and disposal of anticancer drugs should be followed. Several guidelines on this subject have been published (US Dept of Health and Human Services, 1983; Yodaiken et al., 1986). Specific to AMO-01, the following precautionary measures are recommended for the handling and preparation of AMO-01 for injection:

1) The reconstitution and bag transfer procedure should be carried out in a flow hood.

2) The personnel reconstituting AMO-01 drug product should wear polynitrile gloves, safety glasses, disposable gowns, and masks.

3) Due to the high surfactant concentration, careful handling is required during preparation of the dosing formulation and also during administration. Those handling the final prepared AMO-01 formulation should avoid any vigorous agitation at all times as foaming can occur following dilution.

4) All vials, syringes, needles, and other materials, that have come in contact with AMO-01, should be segregated and destroyed by incineration.

6.1.4 Preparation

AMO-01 for injection is supplied as a sterile bulk formulation which requires dilution in sterile 0.9% saline prior to subject administration.

It is planned to use the same sterile bulk formulation qualitatively and quantitatively i.e. 32.84mg/ml drug concentration as developed previously. However bulk vial volumes were reduced to 2.176 ml to deliver a dose of 70mg/vial. A similar dilution factor in 0.9% saline will be performed to arrive at final dosing formulation concentration of 4.49mg/ml. As before, depending on the dose to be administered, several vials could be used for preparation of the infusion bag.

The study drug requires a reconstitution kit to include the following:

- Each single-dose vial of sterile drug product contains 71.4 mg of AMO-01 drug substance in 2.176 ml (including a 2% overfill). This corresponds to a drug content label claim of 70 mg per vial and a drug product volume of 2.134 mL.
- An EVA infusion bag (250-, 500- or 1000-mL, depending on the dose to be administered).
- An administration set consisting of TOTM-plasticized PVC line with a pump connector.
- An extension set consisting of PVC line that is internally coated with PE, an in-line 1.2 micron filter, and an anti-siphon valve.
- A pre-filled syringe or a bag of sterile 0.9% saline.

• An instruction sheet for the preparation of the dosing formulation and for assembly of the infusion kit for administration.

Instructions for final formulation preparation from sterile bulk formulation vials:

The vial content shall be diluted with 13.73 mL of sterile 0.9% saline. Upon dilution, the final volume will be 15.91 mL. This will ensure sufficient dosing formulation to allow for the withdrawal of a minimum isotonic premix volume of 15.59 mL at a concentration of containing 4.49 mg/mL AMO-01, corresponding to the label claim of 70 mg/vial. Depending on the dose to be administered, several vials could be used for the preparation of the infusion bag.

After dilution and gentle mixing (by gently swirling of the vial in a circular motion) the dosing formulation is transferred from the drug product vial into a 1-L disposable sterile bottle (all vials required to prepare an infusion bag are pooled in a single disposable sterile bottle). Using a peristaltic pump the dosing formulation in the disposable sterile bottle is transferred into a 250-mL, 500-mL or 1-L ethyl-vinyl acetate (EVA) or polypropylene (PP) infusion bag. The filled infusion bag is then connected to a pump for continuous infusion.

